4.4. Data Collection

Prior to the start of data collection, the lead investigator of each participating site will have received the Study Protocol and a copy of the CRF for reference. Once the study protocol has been approved by the relevant regulatory body and ethics committee (if applicable) in each country and contracts are

finalised, an initiation telephone call will be organised with the lead investigator in each participating site.

All CRFs received will be tracked and logged on a central database before being processed by Adelphi Real World (ARW) Data Management teams. Sites will regularly be followed-up in order to facilitate the data collection process.

The following data (but not limited to) will be collected by the site abstractors onto CRFs:

- Patient demographics
- Relevant medical history
- Diagnostic procedures performed
- SVT characteristics
- Initial fondaparinux dose, administration frequency and duration of treatment (planned/actual if known). If a dose other than 2.5mg is prescribed/administered, the rationale for this will be requested
- Absence/presence of DVT and relevant details
- Renal Function.

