4.3. Outcome

The primary outcome measure will be the proportion of patients for whom **both** an ultrasound (or other diagnostic imaging procedure), was performed in order to rule out concomitant DVT prior to patients commencing fondaparinux therapy **and** that the correct dose of fondaparinux (2.5mg or 1.5mg) was prescribed (i.e. adherence to fondaparinux prescribing information – see Appendix 9.1). This will be evaluated overall and in each country.

A sensitivity analysis of the primary outcome will be conducted incorporating the length of the thrombus (>5 cm) and/or its distance from the sapheno-femoral junction (>3 cm), pending the availability of the data.

Secondary outcomes will evaluate the proportion of patients prescribed the correct dose of fondaparinux, as well as those who had an ultrasound (or other diagnostic imaging procedure) performed to rule out concomitant DVT. In addition, when available, the proportion of patients having a thrombus >5 cm and a distance from the sapheno-femoral junction of at least 3 cm will be estimated.

Similar to the primary outcome, these will also be evaluated overall and in each country.

Please note that patient outcome data following fondaparinux prescription will not be collected.

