4.5. Validation Procedures

To ensure the validity of the results, it is necessary that the data collected are of good quality. Any missing data will be sought from, and the accuracy of the records will be checked with the respective site/investigator. Once completed case report forms are received by Adelphi, there begins a process of 'logic checks' with identification of, and raising of queries, and query resolution at site level. The resolved queries will then be checked again before being entered into the data base.

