9. APPENDICES

9.1 Fondaparinux prescribing information

PRESCRIBING INFORMATION FOR USE IN PATIENTS WITH SVT

Treatment of superficial-vein thrombosis

The recommended dose of fondaparinux is 2.5 mg once daily, administered by subcutaneous injection. Patients eligible for fondaparinux 2.5 mg treatment should have acute, symptomatic, isolated, spontaneous superficial-vein thrombosis of the lower limbs, at least 5 cm long and documented by ultrasonographic investigation or other objective methods. Treatment should be initiated as soon as possible following diagnosis and after exclusion of concomitant DVT or superficial-vein thrombosis within 3 cm from the saphenofemoral junction. Treatment should be continued for a minimum of 30 days and up to a maximum of 45 days in patients at high risk of thromboembolic complications. Patients could be recommended to self-inject the product when they are judged willing and able to do so. Physicians should provide clear instructions for self-injection.

Special populations

Renal impairment

Treatment of superficial-vein thrombosis - Fondaparinux should not be used in patients with creatinine clearance <20 ml/min. The dose should be reduced to 1.5 mg once daily in patients with creatinine clearance in the range of 20 to 50 ml/min. No dosage reduction is required for patients with mild renal impairment (creatinine clearance >50 ml/min). The safety and efficacy of 1.5 mg has not been studied.

Hepatic impairment

 Treatment of superficial-vein thrombosis - The safety and efficacy of fondaparinux in patients with severe hepatic impairment has not been studied, therefore fondaparinux is not recommended for use in these patients.

Low body weight

 Treatment of superficial-vein thrombosis - The safety and efficacy of fondaparinux in patients with body weight less than 50 kg has not been studied, therefore fondaparinux is not recommended for use in these patients.

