9.3 Case Report Form

·			OFFICE U	SE ONLY
Superficial Vein Thrombosis (SVT): Case	Record Fo	rm	Doctor Number	Patient Number
Today's date:			 (dd/mm/y	ууу)
Date patient first presented with symptoms:			(dd/mm/y	
Date patient mot precented with symptome.		_ /	(aa/111111/y	,,,,,
Date patient diagnosed:	/	_/	(dd/mm/y	ууу)
Fondaparinux prescribing				
Date fondaparinux first prescribed:	/	_/	(dd/mm/y	yyy)
Fondaparinux dose initially prescribed:	mg			
Planned duration of fondaparinux treatment:	da	ays 🗌 w	veeks (please ✓ if	days or weeks)
Diagnosis				
Was SVT confirmed through imaging?	☐ Yes ☐ N	lo		
If yes, what diagnostic imaging, was performed on	this patient?			
☐ Ultrasound ☐ Venography ☐ C	T Scan	☐ MF	RI	
Other (specify:)			
If 'No', please state how SVT was confirmed:				
If imaging was not performed, please state why:				
Please state location of the SVT:	☐ Left lower	limb □R	ight lower limb	
Please state position of the SVT:	 ☐ Great saph		Lesser saph	enous
·	☐ Tributary		r (
Diagon state length of the CVT			om 🗆 Not	rocarded
Please state length of the SVT:			_	recorded
Please state diameter of the SVT:			_	recorded
Please state distance from sapheno-femoral junctic	Of 1	_ · (cm Not	recorded
Was DVT diagnosed?	☐ Yes ☐ N	lo [Imaging not p	erformed
Was symptomatic PE diagnosed?	☐ Yes ☐ N	lo		

[figure not shown]
OFFICE USE ONLY							
Doctor Number	Patient Number						

Superficial Vein Thrombosis (SVT): Case Record Form

Patient demographics						
Age:	years					
Weight:	Kg					
Gender	☐ Female ☐ Male					
Patient history						
Is there documented evidence that this patient has	renal impairment?:					
	☐ Yes ☐ No ☐ Do not know					
If Yes, Mild Moderate Severe Do	not know					
Serum Creatinine result:	µm/L					
	☐ Not assessed					
Date last calculated	/					
Creatinine Clearance result:	ml/min					
	☐ Not assessed					
Date last calculated	/					
Has this patient been previously treated for DVT, PE and/or SVT?						
	□DVT □PE □SVT					

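### The case report form has no field for dosing frequency, actual duration or the reason for a dose other than 2.5 mg, although Section 4.4 says all three are collected

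*Supplement*

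**What the plan says.** Protocol Section 4.4 sets out what site abstractors will record on the CRF. For treatment, the list gives "Initial fondaparinux dose, administration frequency and duration of treatment (planned/actual if known"). It continues: "If a dose other than 2.5mg is prescribed/administered, the rationale for this will be requested".

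The CRF in Appendix 9.3 has a fondaparinux prescribing block with three entries: the date of first prescription, "Fondaparinux dose initially prescribed" (in mg), and "Planned duration of fondaparinux treatment" (in days or weeks).

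Section 4.3 defines the dose part of the primary outcome as whether "the correct dose of fondaparinux (2.5mg or 1.5mg) was prescribed (i.e. adherence to fondaparinux prescribing information", and points to Appendix 9.1. The prescribing information there states: "The recommended dose of fondaparinux is 2.5 mg once daily, administered by subcutaneous injection". For moderate renal impairment it states: "The dose should be reduced to 1.5 mg once daily in patients with creatinine clearance" between 20 and 50 ml/min.

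On data quality, Section 4.5 says: "Any missing data will be sought from, and the accuracy of the records will be checked with the respective site/investigator".

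**The concern.** The protocol commits to collecting three items that its own form does not ask for. They do not matter equally.

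- **Frequency** bears on the label check. The study answers a commitment made at EU approval to evaluate proper dosing, because the higher DVT doses may raise bleeding risk over an extended course. The dose field does not say whether the figure is per injection or per day. A prescription of 2.5 mg twice daily could be entered as 2.5, and scored adherent. It could also be entered as 5, scored non-adherent, and then could not be told apart from the 5 mg DVT dose. Which happens depends on the abstractor, so the direction of any error is not known.
- **Reason for another dose** enters no endpoint but is needed to interpret non-adherence. It is also promised for 1.5 mg, which counts as correct but is still not 2.5 mg. The renal, DVT and PE fields allow a partial inference. They do not help when they are blank or unknown, when DVT was suspected but not diagnosed, or when the dose was a mistake.
- **Actual duration** enters no endpoint and matters least. It is promised data with nowhere to be written.

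**Working it through.** **Field check.** This is a comparison of Section 4.4 with Appendix 9.3; there is no figure in the plan to reproduce.

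| Item promised in Section 4.4 | Field in the Appendix 9.3 CRF |
|---|---|
| Initial dose | Present, in mg; per injection or per day not stated |
| Planned duration | Present |
| Administration frequency | Absent |
| Actual duration, if known | Absent; no stop date either |
| Reason for a dose other than 2.5 mg | Absent |

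The diagnosis, demographics and patient history parts of the CRF do not ask for these items. The only request for a reason concerns imaging that was not done. The amendment note in Appendix 9.5 reports changes to renal items on the forms and nothing on these three, so the mismatch stands within the current version.

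**Consequence for the endpoint.** Sections 2 and 4.3 score the dose by strength (2.5 or 1.5 mg), so the endpoint can be computed. Section 4.3 reads that score as adherence to Appendix 9.1, which gives both doses once daily. Nothing on the form can confirm or refute that part.

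**What recording frequency would allow.** The documents give no rate of prescribing other than once daily, so a bias in the adherence estimate cannot be calculated. One can calculate what could be ruled out if frequency were recorded for every patient and none departed from once daily.

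Inputs: 7 patients per physician, and 840 or 532 patients in total and 210 or 133 per country (Table 2, target and minimum); intra-class correlation 0.2 (one of the Table 3 values, given there for adherence; using it for frequency is an assumption).

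- Design effect = 1 + (7 − 1) × 0.2 = 2.2
- Effective sample size n = N / 2.2
- One-sided 95% upper bound with zero events = 1 − 0.05^(1/n)

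| Sample | N | n at design effect 2.2 | Upper bound | Upper bound, no clustering (n = N) |
|---|---|---|---|---|
| Overall, target | 840 | 381.8 | 0.78% | 0.36% |
| Overall, minimum | 532 | 241.8 | 1.23% | 0.56% |
| Per country, target | 210 | 95.5 | 3.09% | 1.42% |
| Per country, minimum | 133 | 60.5 | 4.83% | 2.23% |

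With the form as printed, none of these bounds is available.

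**The case against.** The strongest reply is that no planned analysis uses the three items. The protocol narrows adherence to imaging and dose strength, and it leaves other label elements, such as treatment duration and low body weight, out of the primary endpoint. The doses it worries about (5, 7.5 and 10 mg) show up in the milligram field, abstractors are trained, and nothing suggests that 2.5 mg is prescribed twice daily. This stands in so far as the endpoint can be scored and the harm is unproven. It does not explain why Section 4.4 lists frequency and the form omits it.

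Second, Section 6 already accepts that reason and duration may be missing from charts. That presupposes that someone asks, and it says nothing of frequency. Without a field, an item absent from the chart cannot be told from one never sought.

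Third, queries under Section 4.5 might recover the data. Its wording is broad enough that a query about an unusual dose is possible. But the logic checks it describes start from completed CRFs, no frequency query is specified, and an item the form never requests will not show up as missing.

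Fourth, the zero-event bounds do not measure bias and borrow their correlation from another outcome. Both points are right; the bounds show only what the missing field would have allowed.

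Last, a figure is missing from the extracted CRF text. It falls after the PE question, outside a prescribing block that reads as complete, so it is unlikely to hold these fields.

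**Conclusion.** The concern holds. Three items that Section 4.4 says go onto the CRF have no field in Appendix 9.3, and the dose field lacks a unit of time. The primary endpoint survives as defined. The once-daily part of the label cannot be verified, and reasons for other doses can be only partly inferred.

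The effect on the adherence estimate is unknown in size and direction and may be near zero. The measurable loss is a bound that full recording, with no exceptions found, could have supplied: 0.8% to 1.2% overall and 3.1% to 4.8% per country, target to minimum sample, on the clustering assumption above; 0.4% to 0.6% and 1.4% to 2.2% with no clustering. This should be corrected before data collection, because recovering the items later means reopening charts.

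**What to change.** Change the CRF before data collection:

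- add frequency, with options for once daily, other (specify) and not recorded;
- label the dose field as mg per injection;
- add the reason for a dose other than 2.5 mg, with a not-recorded option;
- add actual duration, if known.

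Keep the milligram-based primary endpoint. Report how many patients have frequency recorded, and add a sensitivity analysis that counts a prescription recorded as other than once daily as non-adherent. If the sponsor judges an item not worth collecting, remove it from Section 4.4 instead.

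The cost is three added lines and one relabelled field on a paper form, slightly longer abstraction, and one extra analysis. Some entries will probably be not recorded: none of the three items was on the feasibility checklist (Appendix 9.2), which asked only about prescribed dose and prescribed duration, and Section 6 already expects gaps in reason and duration.

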4.5. Validation Procedures

To ensure the validity of the results, it is necessary that the data collected are of good quality. Any missing data will be sought from, and the accuracy of the records will be checked with the respective site/investigator. Once completed case report forms are received by Adelphi, there begins a process of 'logic checks' with identification of, and raising of queries, and query resolution at site level. The resolved queries will then be checked again before being entered into the data base.

5. SAMPLE SIZE AND POWER/PRECISION CALCULATIONS

5.1. Sample Size Calculations

As the primary objective of the study is to obtain an estimate of physician adherence to the fondaparinux prescribing information for SVT, overall and per country, a methodology that takes into consideration the study design, i.e. patients nested within each physician and within each site, has been identified. This explicitly recognises the fact that the prescribing for different patients consulting the same physician is unlikely to be independent and will be correlated (the amount of correlation represented by the intra-class correlation coefficient). It is assumed that prescribing for patients consulting different physicians and sites is independent.

For any given total patient sample size, the higher the ratio of the number of participant physicians to the number of patients each physician recruits, the greater the power achieved. The design of the study intends to allow sites some flexibility (in order to ensure site participation) in the number of physicians and number of patients each may recruit. This flexibility is described in Table 2 below with minimum and target numbers defined. Upper limits in terms of the maximum permissible number of patients per physician and the maximum permissible number of physicians per site are also stated.

Table 2: Enrolment - Minimum, Target and Upper Limits Defined

		Enrolment	
	Target	Minimum	Upper limit
Physicians per country	30*	19	30*
Patients per physician	7	7	10
Patients per country	210*	133	210*
Physicians per site	2	1	5
Patients per site	14	7	20
Sites per country	15*	10	15*
Countries	4	4	4
Total No. Patients	840	532	840

^{*} Average across all countries

The patient sample calculations were based on using the technique described by Emrich and Piedmonte [6] contained within the R statistical package "mvtBinaryEP" [7]. Correlated binary data for a specific user-entered intraclass correlation coefficient could be generated.

Monte Carlo simulations generating such correlated binary data (of the specified intra-class correlation, of the specified sample size, N, and assuming an underlying population probability of adherence of 0.8) were performed. For each simulated data set a Generalised Estimating Equation, GEE, containing a constant term was applied and the 95% confidence interval around the computed average percent adherence prediction was calculated. An indicator variable was created for each simulated data set which took the value 1 if the lower 95% confidence interval just described was above 60% and took the value 0 otherwise. The mean value of this indicator variable was then calculated across all simulation runs and represents the power of achieving a lower bound greater than 60% (given an assumed adherence rate of 80% and a specified intra-class correlation) from the stated sample size/mix.

Table 3 below demonstrates how the power can vary for the same patient sample size of 210 by varying the intra-class correlation and/or the mix of number of physicians and patients managed per physician. The higher the intra-class coefficient the greater the benefit from increasing the number of physicians selected and decreasing the number of patients managed per physician to generate the same total patient base. With this in mind it has also been decided that no one physician should provide more than ten patients to the study (see appendix 9.4).

Table 3: Power Calculations for Minimum and Target Physician Numbers with varying intra-class correlations

	Intra-class correlation	Power
Scenario 1 (210 patients)	0.1	0.998
30 physicians, 7 patients each	0.2	0.974
total 210 patients	0.25	0.963
	0.3	0.937
Scenario 2 (210 patients)	0.1	0.994
21 physicians, 10 patients each	0.2	0.950
total 210 patients	0.25	0.916
	0.3	0.874
Scenario 3 (180 patients)	0.1	0.981
18 physicians, 10 patients each	0.2	0.900
total 180 patients	0.25	0.854
	0.3	0.807
Scenario 4 (Minimum sample)	0.1	0.964
19 physicians, 7 patients each	0.2	0.891

0.804

total 133 patients	0.25	0.846

The power results achieved for the scenarios in Table 3 show that the minimum sample required to still achieve a power ≥0.8 can be achieved by recruiting 10 sites (9 sites with 2 physicians per site and 1 site with 1 physician) with each physician reporting on 7 patients, resulting in a total of 133 patients. It is therefore thought acceptable to implement the targeting scheme with lower limits imposed as detailed in Table 3 ('Minimum sample'). Analysing all four countries will increase the sample size to 840 (4x210; best case scenario) or to 532 (4x133; worst case scenario) and will clearly improve the power beyond that of a single country. Therefore the power for all four countries will exceed 0.8.

0.3

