5.2.1. Primary Analyses

Adherence estimates with confidence intervals will be derived using generalised estimating equations (GEE) overall and for each country [8]. The GEE will explicitly take into account the nesting of patients, per physician, within a medical practice.

Adherence in the current study will be defined as performing CUS, or other diagnostic imaging procedure, in order to rule out concomitant DVT prior to patients commencing fondaparinux therapy and ensuring that the recommended dose of fondaparinux is prescribed.

A sensitivity analysis will be conducted incorporating the length of the thrombus and the distance of the thrombus from the sapheno-femoral junction into the primary endpoint if the data is available.

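### The per-country power of at least 0.8 at the minimum sample assumes that physicians at one site are independent, while the planned GEE allows for nesting within practice; at ICC 0.3 the claim has almost no margin

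*Supplement*

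**What the plan says.** Section 5.1 describes patients as nested in physicians and in sites, and then adopts a simpler planning assumption: "It is assumed that prescribing for patients consulting different physicians and sites is independent". Table 3 accordingly varies one ICC, with physicians as the clusters. Each simulated data set was generated "assuming an underlying population probability of adherence of 0.8", and then "a Generalised Estimating Equation, GEE, containing a constant term was applied". A run counted as a success when the lower 95% limit exceeded 60%.

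From Table 3, Section 5.1 concludes that "the minimum sample required to still achieve a power ≥0.8 can be achieved by recruiting 10 sites", nine of them with two physicians and one with a single physician, at seven patients each (133 patients). The supporting figure at the highest ICC, 0.3, is 0.804.

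For the primary analysis, Section 5.2.1 says: "The GEE will explicitly take into account the nesting of patients, per physician, within a medical practice". Estimates are to be given overall and for each country.

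Table 2 sets a minimum of 7 patients per physician and an upper limit of 5 physicians per site. Its row "Patients per site" has an upper limit of 20.

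**The concern.** The design places most physicians in pairs within sites. Imaging before treatment is one of the two components of the primary outcome (Section 4.3), and the protocol treats imaging largely as a property of the site. The site identification survey (Section 4.1) asks about diagnostic tools in each site, and question 2 of the site assessment survey asks whether the clinical setting has routine imaging access. Two physicians at one site share that access, so some correlation between their patients is plausible.

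If it exists, the effective number of clusters is nearer 10 than 19, and the power that justifies the 10-site floor is overstated. Per-country adherence is part of the primary outcome, so good pooled power does not settle the matter. If the intervals were clustered on physician only, as Table 3 implies, the reported country intervals would be too narrow.

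**Working it through.** **Inputs from Section 5.1:** true adherence 0.80; success if the lower 95% limit is above 0.60; intercept-only GEE; minimum sample of 19 physicians × 7 patients = 133, in 9 sites of two physicians and 1 site of one; target of 15 sites × 2 physicians × 7 patients = 210. **Assumed, because the documents give no value:** the correlation between patients of different physicians at the same site, rs.

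**Method.** Correlated binary data from thresholded normals (the Emrich-Piedmonte approach), logit-scale interval with a sandwich standard error, 40,000 data sets per cell unless stated. Two variants are shown: A, the uncorrected sandwich; B, the variance multiplied by k/(k−1), with k the number of clusters.

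**Step 1: reproduce the plan.** With independent physicians as clusters, variant B gives 0.809 against the stated 0.804 at ICC 0.3, and all 16 cells of Table 3 agree within 2 points. Variant A gives 0.825. Table 3 is therefore sound under its own assumption.

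**Step 2: add same-site correlation and cluster on site.** Minimum sample, ICC 0.3:

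| rs | A | B |
|---|---|---|
| 0 | 0.833 | 0.805 |
| 0.01 | 0.825 | 0.793 |
| 0.02 | 0.816 | 0.784 |
| 0.05 | 0.786 | 0.752 |
| 0.10 | 0.743 | 0.707 |
| 0.15 | 0.708 | 0.671 |
| 0.20 | 0.669 | 0.630 |
| 0.30 | 0.603 | 0.562 |

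Other cells (A / B):
- Minimum sample, ICC 0.2 (stated 0.891): 0.863 / 0.837 at rs 0.05; 0.816 / 0.785 at rs 0.10; 0.734 / 0.698 at rs 0.20.
- Minimum sample, ICC 0.1 (stated 0.964): 0.89 / 0.87 even at rs 0.10, that is, equal to the physician ICC.
- Target sample, ICC 0.3 (stated 0.937; 20,000 data sets): 0.87 / 0.85 at rs 0.15; 0.78 / 0.75 at rs 0.30.
- Four countries pooled at the minimum, ICC 0.3, rs 0.15 to 0.30: above 0.99 (5,000 data sets).

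**Step 3: hand check of direction.** For two physicians per site the design effect is 1 + 6 × 0.3 + 7 × rs, which is 2.8, 3.85 and 4.9 for rs 0, 0.15 and 0.30. (It is slightly too large here, since one site has a single physician.) The effective sample size is 133/2.8 = 47.5, 133/3.85 = 34.5 and 133/4.9 = 27.1. The logit distance from 0.6 to 0.8 is 1.386 − 0.405 = 0.981, and the logit standard error is √(1/(0.16 × n_eff)) = 0.363, 0.425 and 0.480. Power is Φ(0.981/SE − 1.96) = 0.77, 0.64 and 0.53. The formula runs below the simulation, but the fall is the same in kind.

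**Step 4: physician-only clustering.** At the minimum sample and ICC 0.3, power looks nearly unchanged (variant A: 0.80 at rs 0.15, 0.78 at rs 0.30). Nominal 95% intervals, however, cover about 88–89% and 82–84% respectively, against about 93% at rs 0.

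**Step 5: Table 2.** 3 physicians × 7 patients = 21, above the limit of 20 per site. No site can use more than two physicians, so the stated limit of 5 is unreachable (5 × 7 = 35).

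**The case against.** The strongest reply is that nothing was miscalculated. Independence is stated openly, Table 3 reproduces, and an analysis that allows for more correlation than its power model is a mismatch rather than a contradiction. That stands. Section 5.2.1 also leaves the cluster unit and working correlation unnamed, so site clustering is one reading of it. Such detail may properly sit in an analysis plan that is not shown, and it is not counted here as an omission.

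Three stronger inferences are tempting, and the documents do not support them:

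- *That any site correlation takes power below 0.8.* On the uncorrected sandwich, power at ICC 0.3 is still 0.816 at rs 0.02 and crosses 0.8 only between 0.02 and 0.05. On the variant that matches Table 3, it is already 0.793 at rs 0.01.
- *That the true power is some particular lower figure, such as 0.60 to 0.71.* That range needs rs of 0.30 to 0.15 with the uncorrected sandwich. The upper value of rs makes colleagues at a site as alike as one physician's own patients, which is the extreme case.
- *That the study as a whole is underpowered.* The shortfall is confined to country-level estimates at the higher ICCs or larger site correlations. Pooled power is unaffected.

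It is also fair that the aim is estimation and that 60% is not used as a decision rule in the analysis. By the Step 3 figures, the expected half-width 1.96 × √(0.16/n_eff) goes from 0.11 (n_eff 47.5) to 0.13 (34.5) or 0.15 (27.1). That is a real loss but a moderate one. Lastly, clustering on site is no complete cure: with 10 clusters, uncorrected intervals cover only about 90% at rs 0.15 and 91% at rs 0.

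**Conclusion.** The concern holds in a limited form. The statement that 10 sites and 133 patients keep per-country power at 0.8 or more depends on zero correlation between physicians at a site, an assumption inconsistent with the nesting that the primary analysis is meant to respect. The margin at ICC 0.3 is 0.804 − 0.8 = 0.004.

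With same-site correlation assumed between 0.05 and 0.30, power at the minimum sample and ICC 0.3 is about 0.79 down to 0.56, depending on that value and on the sandwich correction. At ICC 0.2 with same-site correlation 0.10 to 0.20 it is about 0.82 to 0.70. At ICC 0.1 it stays above 0.8. At the target sample and ICC 0.3 it is about 0.87 to 0.75 for same-site correlation 0.15 to 0.30. All of these rest on an assumed site correlation, so they show sensitivity and are not estimates of the actual power. The Table 2 conflict is a separate, minor point that follows from arithmetic alone.

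**What to change.** 1. Re-run Table 3 with two correlations, within physician and between physicians at the same site, setting the latter to zero, half of and equal to the physician ICC.
2. Cluster the GEE on site, with a small-sample correction because each country has only 10 to 15 clusters, and use the same interval in the simulation. A strict correction costs power even without site correlation: a t interval on 9 degrees of freedom with the k/(k−1) factor gives 0.70 at rs 0, 0.55 at 0.15 and 0.44 at 0.30 (minimum sample, ICC 0.3).
3. Restate per-country power as the resulting range, and keep the unqualified claim of more than 0.8 for the pooled estimate only.
4. Reconcile Table 2, for example by lowering the limit to two physicians per site, which fits the other limits (2 × 10 = 20). Cutting the minimum to four patients so that 5 × 4 = 20 fits would be a poor choice, because it concentrates patients in fewer sites. At 140 patients and ICC 0.3, seven sites of 5 × 4 give 0.69 and 0.52 (variant A, rs 0.15 and 0.30), against 0.72 and 0.61 for ten sites of 2 × 7.

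The cost is a re-run of an existing simulation, revised wording, a less favourable stated per-country power and somewhat wider country intervals. No extra patients are needed.
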